This amended protocol (amendment 04) is considered to be non-substantial based on the criteria set forth in Article 10(a) of Directive 2001/20/EC of the European Parliament and the Council of the European Union because it does not significantly impact the safety or physical/mental integrity of participants, nor the scientific value of the study.

OVERALL RATIONALE FOR THE AMENDMENT

The protocol is amended to modify the type of interim analysis.

Protocol amendment summary of changes table

Section # and Name	Description of Change	Brief Rationale
2.3.1 Risk assessment	[REDACTED]	Risk assessment description of this case in the context of the study.
1.1 Synopsis 4.1 Overall design 6.1 Study intervention(s) administered	Sentence added for non-IMPs: "The class of reliever medication should not change during the study."	Background therapy should remain stable throughout the study, clarification added for reliever medications.
6.8.4 Prohibited concomitant medication	Systemic steroids use allowed for up to 7 consecutive days.	Systemic steroids for treatment of conditions other than asthma are allowed for up to 7 consecutive days.
7.2 Participant discontinuation/withdrawal from the study	A note has been added: "Safety follow-up (EOS, end-of-study) visit should be performed after [REDACTED] after the last IMP."	Clarification.

Section # and Name	Description of Change	Brief Rationale
1.1 Synopsis and 9.2.2 Primary endpoint(s) analysis	Primary endpoint supplementary analysis of intercurrent events was detailed.	Clarification.
1.1 Synopsis and 9.2.3 Secondary endpoint(s) analysis	Modification of “supportive” analyses of intercurrent events to “supplementary” analysis.	Harmonization.
10.2 Appendix 2: Clinical Laboratory tests	Addition of the following tests to the list: uric acid, total cholesterol, albumin, lactate dehydrogenase, chloride, bicarbonate.	List of the study central laboratory tests was incomplete.
10.6 Appendix 6: Liver and other safety: suggested actions and follow-up assessments	Update of the management of increase in ALT as per Sanofi standard.	Clarification.
Section 10.12 Appendix 12: Protocol amendment history	The text of summary of changes for Protocol amendment 03 is added.	Appendix 12 is updated to reflect the document history of previous amendment.
Throughout the document	Small changes (editorial) have been made.	Clarification.

TABLE OF CONTENTS

AMENDED CLINICAL TRIAL PROTOCOL 04	1
PROTOCOL AMENDMENT SUMMARY OF CHANGES	2
TABLE OF CONTENTS	4

1 PROTOCOL SUMMARY

1.1 SYNOPSIS

Protocol title:

A randomized, double-blind, placebo-controlled, parallel-group, dose ranging study to assess the efficacy, safety, and tolerability of subcutaneous amlitelimab in adult participants with moderate-to-severe asthma

Brief title:

Dose ranging study of amlitelimab in adult participants with moderate-to-severe asthma

Rationale:

Amlitelimab (also known as SAR445229 or KY1005), a human anti-OX40 ligand (OX40L, CD252) monoclonal antibody (mAb) (subclass IgG4PE kappa) that binds OX40L to block the interaction with its receptor, OX40 (CD134), is an investigational drug being developed for the treatment of immune-mediated diseases. This study will explore the efficacy and safety of amlitelimab in adult participants with moderate-to-severe asthma.

Objectives and endpoints:

Objectives	Endpoints
Primary	

To evaluate the efficacy of different doses of amlitelimab compared to placebo in participants with moderate-to-severe, uncontrolled asthma.	
Annualized rate of severe exacerbation events over 48 weeks, defined as:
Worsening of asthma requiring the use of systemic corticosteroids for ≥ 3 days or, in the case of a stable maintenance regimen of oral corticosteroids (OCS) for the treatment of asthma, a doubling of the dose for 3 or more days; orHospitalization or emergency room visit because of asthma, requiring systemic corticosteroids
Secondary	

To evaluate the effects of amlitelimab compared to placebo on lung function as measured by forced expiratory volume in 1 second (FEV1)To evaluate the effects of amlitelimab on Asthma Control Questionnaire 5 (ACQ-5)	
Change from baseline in pre-bronchodilator (BD) FEV1 at Week 48 (key secondary endpoint)Change from baseline in post-BD FEV1 at Week 48The absolute change in the percent predicted FEV1 from baseline to Week 48 (pre-BD and post-BD)Change from baseline in ACQ-5 score at Week 48 (key secondary endpoint)Change from baseline in ACQ-5 score at Weeks 2, 4, 8, 12, 24, 36, and 60

Objectives	Endpoints

 To evaluate the effects of amlitelimab on time to first severe exacerbation event To evaluate the effects of amlitelimab on other spirometry assessments To evaluate the effects of amlitelimab on fraction of exhaled nitric oxide (FeNO) To evaluate the effects of amlitelimab compared to placebo on reducing the incidence of "loss of asthma control" (LOAC) events 	
 Time to first severe exacerbation event Change from baseline in pre-BD and post-BD FEV1 and other lung function measurements (peak expiratory flow [PEF], forced vital capacity [FVC], and forced expiratory flow [FEF] 25-75%) at each spirometry endpoint Change from baseline in FeNO at Weeks 2, 4, 8, 12, 16, 24, 36, 48 and 60 Annualized rate of LOAC events, during 48 weeks of treatment, defined by one or several of the following criteria: 
 A 30% or greater reduction from baseline in morning PEF on 2 consecutive days. ≥6 additional reliever puffs of short-acting beta 2-agonists (SABA) OR ≥4 additional puffs of low-dose ICS/formoterol in a 24-hour period (compared to baseline) on 2 consecutive days Increase in ICS ≥4 times than the Visit 2 dose Worsening of asthma requiring the use of systemic corticosteroids for ≥3 days or, in the case of a stable maintenance regimen of OCS for the treatment of asthma, a doubling of the dose for 3 or more days Hospitalization or emergency room visit because of asthma, requiring systemic corticosteroids severe exacerbation event

 To evaluate the effects of amlitelimab on time to first LOAC event To evaluate the effects of amlitelimab on asthma symptoms To evaluate the effects of amlitelimab on reducing the incidence of severe asthma exacerbations requiring hospitalization or emergency room or urgent care visit Assess the effect of amlitelimab on BD therapy To evaluate the pharmacokinetics (PK) of amlitelimab and anti-drug antibodies to amlitelimab in participants with asthma 	
 Time to first LOAC event Change from baseline in the Asthma Daytime Symptom Diary (ADSD) 6-item daily morning score and in the Asthma Nighttime Symptom Diary (ANSND) 6-item daily evening scores at Weeks 2, 4, 8, 12, 24, 36, 48, and 60 Annualized rate of severe asthma exacerbations requiring hospitalization or emergency room or urgent care visit during 48 weeks of treatment Change from baseline in the numbers of inhalations/day of SABA or low-dose ICS/formoterol for symptom relief at Weeks 2, 4, 8, 12, 24, 36, 48, and 60 Serum amlitelimab concentrations measured throughout the study Incidence of anti-amlitelimab antibody positive response

Objectives	Endpoints

 To evaluate the safety of amlitelimab in participants with asthma To evaluate the effects of amlitelimab on participant reported outcomes (PROs) To evaluate the effects of amlitelimab on ACQ-6 and ACQ-7 	
 Percentage of participants with treatment-emergent adverse events (TEAEs), including local reactions, adverse events of special interest (AESIs), serious adverse events (SAEs) Incidence of potentially clinically significant laboratory test, vital signs, and ECG abnormalities in the treatment period Change from baseline in Asthma Quality of Life Questionnaire with Standardized Activities (AQLQ (S)) Self-Administered Score at Week 48 (key secondary endpoint) AQLQ (S) Self-Administered Score at Weeks 2, 4, 8, 12, 24, 36, and 60 Change from baseline in St. George's Respiratory Questionnaire (SGRQ) at Weeks 2, 4, 8, 12, 24, 36, 48, and 60 Proportion of participants with a decrease from baseline of at least 4 points in SGRQ total score at Week 48 Change from baseline in ACQ-6 score and ACQ-7 at Weeks 2, 4, 8, 12, 24, 36, 48, and 60

Overall design:

This is a Phase 2, global, multicenter, randomized, double-blind, placebo-controlled, parallel-group, dose-ranging study to assess the efficacy, safety, and tolerability of add-on therapy with subcutaneous (SC) amlitelimab in adult participants (aged 18-75 years, inclusive) with moderate-to-severe asthma. All eligible participants will be randomized into (2:2:1:2) ratio and treated for 60 weeks, receiving a SC administration of amlitelimab every 4 weeks (Q4W) for the first 6 doses and every 12 weeks (Q12W) thereafter or matching placebo according to one of the following doses:

- Amlitelimab 250 mg with 500 mg loading dose on Day 1
- Amlitelimab 125 mg with 250 mg loading dose on Day 1
- Amlitelimab 62.5 mg with 125 mg loading dose on Day 1
- Matching placebo

Randomization will be stratified by Screening Visit 1 eosinophil count (<300 cells/ μ L and \geq 300 cells/ μ L), number of severe asthma exacerbations (as defined above in the 'objectives and endpoints' table) in the previous 12 months (=1 exacerbation or >1 exacerbations) and by region.

To avoid recruiting a skewed population due to competing studies, alerts will be built into the interactive voice/web response system (IVRS/IWRS) to limit enrolling participants in the following 2 stratification groups:

- Only 1 severe asthma exacerbation in the previous 12 months: not more than approximately 50% of participants (210 participants).
- Eosinophils <300 eosinophils/ μ L: not more than approximately 50% of participants (210 participants).

Amlitelimab will be administered as add-on therapy to inhaled corticosteroid (ICS) in combination with a second controller medication (eg, long-acting beta agonist [LABA], leukotriene receptor antagonist [LTRA], methylxanthines, long-acting muscarinic antagonist [LAMA]) with or without oral prednisone for the maintenance treatment of asthma. Participants requiring a third controller are allowed to participate in this study (please see [Section 5.1](#)), which consists of three periods:

- Screening period (up to 4 weeks) to determine whether participants meet entry criteria and to establish the level of asthma control before randomization
- Randomized treatment period (approximately 60 weeks)
- Follow-up period (approximately 12 weeks) to monitor participants after treatment
 - Eligible participants who complete the treatment period will be offered the opportunity to participate in the long term safety (LTS) study with amlitelimab. Participants subsequently enrolled in the LTS study will not participate in the follow-up period of this trial but will have a follow up period after the LTS study.

Brief summary:

This is a parallel, Phase 2, global, multicenter, randomized, double-blind, placebo-controlled, dose-ranging, four-arms study for treatment.

The purpose of this study is to assess the efficacy, safety, and tolerability of add-on therapy with amlitelimab in adult participants with moderate-to-severe asthma.

Study details include:

- The study duration (per participant) will be up to approximately 76 weeks for participants not going into LTS study and will be up to approximately 64 weeks for participants going into LTS study.
- The randomized treatment duration will be up to approximately 60 weeks.
- The scheduled number of visits will be 13.

Number of participants:

Approximately 420 participants will be randomized to study intervention.

Note: Randomized participants are all participants from screened participants who have been allocated to an intervention by IVRS/IWRS regardless of whether the intervention was received or not.

Intervention groups and duration:

All participants will receive SC administration of amltelimab 250 mg with 500 mg loading dose on Day 1, or 125 mg with 250 mg loading dose on Day 1, or 62.5 mg with 125 mg loading dose on Day 1 or matching placebo, Q4W for the first 6 doses and Q12W thereafter until Week 48 for all arms.

Study intervention(s)

Amltelimab and placebo matching amltelimab are supplied as solutions in vials that are visually indistinguishable.

Investigational medicinal product(s)

- Formulation:
 - Amltelimab: a 125 mg/mL amltelimab solution in a vial to deliver up to 125 mg of amltelimab in a 1 mL injection.
 - Placebo matching amltelimab: identical formulation to the active amltelimab formulation without amltelimab, in a vial to deliver placebo in a up to 1 mL injection.
- Route(s) of administration: SC injection, to abdomen or outer thigh. IMP should not be administered at the exact site of a recent injection or in areas which in the Investigator's opinion are not suitable (eg, tender, bruised, red or hard).
- Dose regimen:
 - Amltelimab 250 mg with 500 mg loading dose treatment group: one initial loading dose of 500 mg of amltelimab (two 2 mL injections of 250 mg of amltelimab) on Day 1, followed by one 2 mL injection of 250 mg of amltelimab Q4W until Week 20 (inclusive) and Q12W starting from Week 24 and thereafter until Week 48.
 - Amltelimab 125 mg with 250 mg loading dose treatment group: one initial loading dose of 250 mg of amltelimab (two 2 mL injection of 125 mg of amltelimab) on Day 1, followed by one 2 mL injection of 125 mg of amltelimab Q4W until Week 20 (inclusive) and Q12W starting from Week 24 and thereafter until Week 48.
 - Amltelimab 62.5 mg with 125 mg loading dose treatment group: one initial loading dose of 125 mg of amltelimab (two 2 mL injections of 62.5 mg of amltelimab) on Day 1, followed by one 2 mL injection of 62.5 mg of amltelimab Q4W until Week 20 (inclusive) and Q12W starting from Week 24 and thereafter until Week 48.
 - Placebo treatment group: one initial dummy loading dose of only placebo (two 2 mL injections of placebo matching amltelimab) on Day 1, followed by one 2 mL injection of placebo matching amltelimab Q4W until Week 20 (inclusive) and Q12W starting from Week 24 and thereafter until Week 48.

Noninvestigational medicinal products

On a daily basis throughout the study, the participant will use an electronic diary (eDiary) to record daily use of ICS in combination or administered concurrently with other controllers as used just prior to screening.

The recognized asthma controllers for the study will include the following 5 classes: ICS, LABA, LAMA, anti-leukotrienes and methylxanthines. Please refer to [Section 10.10.3](#) for a list of commonly used asthma controller medication.

- Screening period:

Prior to screening, participants must be on a stable background therapy for at least 3 months, composed of medium to high dose ICS (≥ 500 µg fluticasone propionate daily or comparable ICS dosage up to a maximum of 2000 µg/day of fluticasone propionate or clinically comparable ([1], see [Section 10.10.1](#)) in combination with a second controller medication (eg, LABA, LTRA, LAMA, methylxanthines) with stable doses ≥ 1 month prior to Visit 1. Participants requiring a third controller are allowed to participate in this study. The third controller should also be used for at least 3 months with a stable dose ≥ 1 month prior to Visit 1. For Japan, please see [Section 10.8](#) for details.

Route of administration: Oral inhalation

If on chronic oral corticosteroid (OCS) treatment for the maintenance treatment of asthma, up to a maximum of 15 mg prednisone or equivalent daily or 30 mg every other day, must be on stable dose for ≥ 1 month prior to Visit 1 (see [Section 10.10.2](#) for comparison of systemic glucocorticoid preparations).

Route of administration: Oral tablets.

- Randomized treatment period:

During this period, participants will continue to take their controller medication(s) used during the screening period and will use an eDiary to record daily use. The dose and regimen should not be changed, except for the OCS, for which the dose could be changed per Investigator medical judgement.

- Follow-up period:

Upon completing the randomized treatment period, participants will proceed to be treated with the controller medication regimen and dose used during the randomized treatment period, which could be adjusted based on the medical judgment of the Investigator of the participants' asthma control status.

Reliever Medication

Participants may administer SABA metered dose inhaler (MDI) and dry powder inhaler (DPI) as reliever medication as needed during the study. Nebulizer solutions may be used as an alternative delivery method, if previously used by the patient. Alternatively, low-dose ICS/formoterol may be used as reliever medication, per Global Initiative for Asthma (GINA) 2021 recommendation (2) and Investigator discretion. The class of reliever medication should not change during the study. Reliever medication use will be recorded in the eDiary. Please refer to [Section 6.8.2](#) for a list of commonly used asthma reliever medications.

Route of administration: Oral inhalation

Devices:

Sanofi or a designee will provide standard study supplies to the sites for the execution of trial-related activities. These supplies include the following:

- Electronic Diaries
- Spirometry devices
- Electronic Spirometry devices for remote spirometry and PEF measurement
- Digital inhalers to measure the reliever use (in certain countries, optional)
- Impulse oscillometry devices
- FeNO measurement devices
- Laboratory kits including tubes, needles, dipsticks
- IMP transportation material as described in the Pharmacy Manual

Instructions on material supply, tracking, return and destruction will be provided in vendor manuals.

Duration of study intervention

Eligible participants who complete the treatment period will be offered the opportunity to participate in the LTS study with amltelimab. Participants subsequently enrolled in the LTS study will not participate in the follow-up period of this trial but will have a follow up period after the LTS study.

Total duration would be approximately 76 weeks for participants not going into LTS study, including up to 4 weeks for screening period, approximately 60 weeks for randomized treatment period, and approximately 12 weeks for follow up period.

Total duration would be approximately 64 weeks for participants going into LTS study, including up to 4 weeks for screening period and approximately 60 weeks for randomized treatment period, then enrollment into LTS study.

Statistical considerations:

[REDACTED]

[REDACTED]

[REDACTED]

[REDACTED]

[REDACTED]

[REDACTED]

[REDACTED]

[REDACTED]

[REDACTED]

[REDACTED]

[REDACTED]

[REDACTED]

[REDACTED]

[REDACTED]

[REDACTED]

[REDACTED]

[REDACTED]

[figure not shown]
[illegible]

A Data Monitoring Committee (DMC) has been appointed for this study. The DMC (board) is a group of independent physician and scientist experts who are appointed to monitor the safety and scientific integrity of a human research intervention, and to make recommendations to the Sponsor regarding the stopping of a study for efficacy, for harms, or for futility. The composition of the committee is dependent upon the scientific skills and knowledge required for monitoring the particular study.

The DMC procedures and safety data to be reviewed by the DMC are described in the DMC charter. In the above capacities, the DMC is advisory to the Sponsor. The Sponsor is responsible for promptly reviewing and for taking into account in a timely manner the recommendations of the DMC in terms of trial continuation with or without alterations or of potential trial termination.

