- f Clinical laboratory testing at Screening (Visit 1) will include a hepatitis screen covering hepatitis B surface antigen (HBs Ag), hepatitis B surface antibody (HBs Ab), total hepatitis B core antibody (HBc Ab), IgM antibody to hepatitis B core antigen (IgM HBc Ab), hepatitis C virus antibodies (HCV Ab), HIV screen (anti-HIV-1 and HIV-2 antibodies). In case of results showing HBs Ag (negative), and HBc Ab Total (positive), HBV DNA testing will be performed prior to randomization to rule out a false positivity to clarify the serological status. In case of results showing HCV Ab (positive), HCV RNA testing will be performed to rule out a false positivity. Please refer to Table 7 in Section 8.2.4.
- g Hematology: hemoglobin, hematocrit, platelet count, total white blood cell (WBC) count with five-part differential count, and total red blood cell count. Serum chemistry: creatinine, blood urea nitrogen, glucose, uric acid, total cholesterol, total protein, albumin, total bilirubin (in case of values above the normal range, differentiation in conjugated and non-conjugated bilirubin), alanine aminotransferase, aspartate aminotransferase, alkaline phosphatase, lactate dehydrogenase, electrolytes (sodium, potassium, chloride), bicarbonate, and creatine phosphokinase. The blood sample for serum chemistry must be taken with the participant in fasting state which means no intake of any food or drink except for water for at least 8 hours (if the visit can only be done at a different time of the day and the participant is not fasting, then he/she should be advised to eat light food and the site should document that serum chemistry was not obtained under fasting conditions). Urinalysis will include specific gravity, pH, glucose, ketones, blood, protein, nitrite, leukocyte esterase, urobilinogen, and bilirubin. If any urinalysis parameter on the dipstick is abnormal, a urine sample should be sent to the central laboratory for quantitative measurement. If urinalysis sample is abnormal for protein and/or red blood cells, microscopic analysis will be performed by the central laboratory.
- h The ECGs will be obtained prior to laboratory assessments and prior to spirometry.

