Amlitelimab (also known as KY1005 or SAR445229) binds OX40L and blocks interaction with its receptor, OX40. The engagement between OX40 and OX40L occurs during the T-cell-antigen-presenting cell (APC) interaction, after antigen recognition, and provides essential signals for the generation and survival of Tmem, the enhancement of the T helper (Th) cell (such as Th1, Th2, Th17 and Th22) response and the prolongation of inflammatory responses (17). Asthma is a heterogeneous disease, with approximately half of asthma patients showing evidence of Type 2 inflammation, elevated Th2 cytokines (IL-5, IL-13, and IL-4) and eosinophilic infiltration, the target of current biologics. Few effective therapies are currently in place for asthma patients showing evidence of non-eosinophilic, Type 2-low inflammation (18).

Amlitelimab data collected to this stage of development in two healthy volunteer studies and a single Phase 2a study in participants with moderate-to-severe atopic dermatitis (AD) suggest an unremarkable safety profile with no specific identified risk from nonclinical/clinical programs so far.

The objective of this DRI17509 study is to assess the efficacy and safety of amlitelimab, a human anti OX40L mAb, in participants with moderate-to-severe asthma which is not well controlled on ICS in combination with other controller medication(s) with or without OCS therapy.

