2.2 BACKGROUND

Overview of amlitelimab

Amlitelimab binds OX40L to block the interaction with its receptor, OX40 (CD134). The Fc regions were modified to the IgG4PE variant to reduce Fc receptor binding and stabilize the antibody hinge region. The resulting molecule is therefore expected to have null effector function (known not to deplete target cells) and would not undergo fragment antigen binding arm exchange as has been reported for natural IgG4.

OX40L is inducibly expressed on professional antigen presenting cells, such as B cells, dendritic cells (DC) and macrophages upon activation (19). Other cells such as endothelial cells, smooth muscle cells, mast cells and natural killer cells can also be induced to express OX40L (20). OX40L interacts “monogamously” with OX40, which is expressed on activated T cells (21), CD4 and CD8 T cells, inducing differentiation towards Th2, Th1, Th17, and Th22. The OX40/OX40L axis has also been shown to enhance the proliferation and activation of Tmem and abrogate

forkhead box P3 positive regulatory T cells (Treg) function (22). OX40-OX40L interaction is also necessary for the differentiation of activated B cells into highly Ig-producing cells.

The interaction between OX40 and OX40L occurs during the T cell DC interaction, following inducible expression of OX40L on DCs between hours and days after antigen recognition. After disengaging from DCs, the OX40 expressing T cell may then interact with other OX40L expressing cells, which in turn provide essential signals for the generation of Tmem with a drive to Th2 polarization and the prolongation of the inflammatory responses. OX40 signals render T cells resistant to Treg cell mediated suppression and furthermore, OX40 signaling in Treg cells directly inhibits their suppressive function.

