Serious and opportunistic infections (including Helminthic infections)	
Serious infections are common to immunomodulatory drugs and there is no evidence to suggest these will be exaggerated in the specific case of OX40/OX40L blockade.
 
Since the physiological role of T cells is host defense against infections, treatment with an OX40L blocker may be associated with a risk of reduced control of infections [REDACTED]
 
[REDACTED]
 
[REDACTED]
 
[REDACTED]
 
[REDACTED]
 
in the clinical program to date, including KY1005-CT01 (Phase 1, healthy volunteers) and KY1005-CT02 (Phase 2, participants with moderate-to-severe atopic dermatitis [AD]).
 
More detailed information is available in the IB.
	
Evaluation for serious infection prior to initiating treatment with the IMP is recommended.
 
Routine monitoring of serious infection via indicative clinical signs and symptoms. If signs or symptoms of clinically important acute infection occur, IMP will be withheld, and the infection managed according to standard of care.
 
Helminthic Infections: Exclusion of participants with chronic or active helminth infections. All such infections should be treated before initiating therapy with the IMP. If participants become infected while receiving the IMP, the IMP should be discontinued until infection is resolved.
 
The following are considered exclusion criteria from study participation:
 
 Known history of or suspected significant current immunosuppression, including history of invasive opportunistic or helminthic infections despite infection resolution or otherwise recurrent infections of abnormal frequency or prolonged duration. Any active or chronic infection requiring systemic treatment within 2 weeks prior to baseline (1 week in the event of superficial skin infections). Active or latent TB infection Active/chronic infections including helminthic infection.

Potential risk of clinical significance	Summary of data/rationale for risk	Mitigation strategy
		
In the event of any infection, Investigators will determine whether temporary or permanent discontinuation of IMP is necessary.
 
To further characterize this potential risk, any severe or opportunistic viral, bacterial, or fungal infection and/or any uncommon, unanticipated or persistent infection (viral, parasitic, bacterial, or fungal) are considered an AESI for amltelimab.

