eGFR (mL/min/1.73m ²) (Estimate of GFR based on an MDRD equation)	<15 (end stage renal disease) ≥ 15 - <30 (severe decrease in GFR) ≥ 30 - <60 (moderate decrease in GFR) ≥ 60 - <90 (mild decrease in GFR) ≥ 90 (normal GFR)	FDA draft Guidance 2010 Pharmacokinetics in patients with impaired renal function-study design, data analysis, and impact on dosing and labeling
Creatinine	$\geq 150 \mu\text{mol/L}$ (Adults) $\geq 30\%$ change from baseline $\geq 100\%$ change from baseline	Benichou C., 1994.
Uric Acid Hyperuricemia Hypouricemia	>408 $\mu\text{mol/L}$ <120 $\mu\text{mol/L}$	Harrison- Principles of internal Medicine 17 th Ed., 2008.
Blood Urea Nitrogen	$\geq 17 \text{ mmol/L}$	

CRITERIA for POTENTIALLY CLINICALLY SIGNIFICANT ABNORMALITIES

for Phase 2/3 studies

(From BTD-009536 – 21-MAY-2014)

Parameter	PCSA	Comments
Chloride	<80 mmol/L >115 mmol/L	
Sodium	≤129 mmol/L ≥160 mmol/L	
Potassium	<3 mmol/L ≥5.5 mmol/L	FDA Feb 2005.
Total Cholesterol	≥7.74 mmol/L	Threshold for therapeutic intervention.
Triglycerides	≥4.6 mmol/L	Threshold for therapeutic intervention.
Lipasemia	≥3 ULN	
Amylasemia	≥3 ULN	
Glucose		
Hypoglycaemia	≤3.9 mmol/L and <LLN	ADA May 2005.
Hyperglycaemia	≥11.1 mmol/L (unfasted); ≥7 mmol/L (fasted)	ADA Jan 2008.
HbA1c	>8%	
Albumin	≤25 g/L	
CRP	>2 ULN or >10 mg/L (if ULN not provided)	FDA Sept 2005.
Hematology		
WBC	<3.0 Giga/L (Non-Black); <2.0 Giga/L (Black) ≥16.0 Giga/L	Increase in WBC: not relevant. To be interpreted only if no differential count available.
Lymphocytes	>4.0 Giga/L	
Neutrophils	<1.5 Giga/L (Non-Black); <1.0 Giga/L (Black)	International Consensus meeting on drug-induced blood cytopenias, 1991. FDA criteria.
Monocytes	>0.7 Giga/L	
Basophils	>0.1 Giga/L	
Eosinophils	>0.5 Giga/L or >ULN (if ULN ≥0.5 Giga/L)	Harrison- Principles of internal Medicine 17 th Ed., 2008.

CRITERIA for POTENTIALLY CLINICALLY SIGNIFICANT ABNORMALITIES

for Phase 2/3 studies

(From BTD-009536 – 21-MAY-2014)

Parameter	PCSA	Comments
Hemoglobin	≤ 115 g/L (Male); ≤ 95 g/L (Female) ≥ 185 g/L (Male); ≥ 165 g/L (Female) Decrease from Baseline ≥ 20 g/L	Criteria based upon decrease from baseline are more relevant than based on absolute value. Other categories for decrease from baseline can be used (≥ 30 g/L, ≥ 40 g/L, ≥ 50 g/L).
Hematocrit	≤ 0.37 v/v (Male) ; ≤ 0.32 v/v (Female) ≥ 0.55 v/v (Male) ; ≥ 0.5 v/v (Female)	

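### The laboratory-safety endpoint cannot count a low lymphocyte value, because SAP Appendix 6 gives the lymphocyte row only an upper limit

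*Protocol*

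**What the plan says.** The safety objective (Protocol 1.1 and Table 2; SAP Table 1) has as one of its endpoints "Incidence of potentially clinically significant laboratory test, vital signs, and ECG abnormalities in the treatment period". The criteria are in SAP Appendix 6 (section 5.6), taken from a sponsor standard for Phase 2/3 studies. The relevant hematology rows, in Giga/L, are:

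- Lymphocytes: above 4.0. There is no other limit.
- Neutrophils: below 1.5 (non-Black) or below 1.0 (Black).
- Platelets: below 100, or 700 and above.
- WBC: below 3.0 (non-Black) or below 2.0 (Black), or 16.0 and above. The comment sets aside increases and then adds "To be interpreted only if no differential count available".
- Monocytes above 0.7; basophils above 0.1; eosinophils above 0.5, or above the laboratory's upper limit where that is at least 0.5.

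Lymphocytes are measured. Protocol 1.3, footnote g, specifies "total white blood cell (WBC) count with five-part differential count", and Protocol Table 13 lists lymphocytes by name.

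On mechanism, Protocol 2.1 says that OX40/OX40L engagement "provides essential signals for the generation and survival of Tmem". The risk table in Protocol 2.3.1 says that "treatment with an OX40L blocker may be associated with a risk of reduced control of infections". Against this, Protocol 2.2 describes the antibody as "known not to deplete target cells".

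The text on the analysis of laboratory variables (SAP 3.6.3.1, Protocol 9.2.6.2) is redacted. The criteria table is legible.

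**The concern.** An incidence endpoint can count only what its criteria define. In Appendix 6 a lymphocyte value is abnormal only when it is high. For a drug that interrupts a T-cell survival signal, the low side is at least as natural a direction to watch, and it is the side that bears on the infection risk the protocol itself names. Other cell lines in the same table do have low limits, so the gap is specific to this row.

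At stake is how complete one stated safety endpoint is in a dose-ranging trial. SAP 3.8 puts laboratory values into the interim analysis, whose purpose includes Phase 3 planning and discussion with health authorities. A reader of the PCSA table could take the lack of any low-lymphocyte entry as reassurance, when the table could not have produced one.

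**Working it through.** The plan has no figure to reproduce here. The check applies the Appendix 6 rows as written to example differential counts.

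**Data the endpoint covers.** "Approximately 420 participants will be randomized to study intervention" SAP Table 10 gives laboratory windows within the treatment period at Weeks 4, 12, 24, 36, 48 and 60, which is 6 time points. With no drop-out, 420 × 6 = 2,520 scheduled lymphocyte values would be collected, and none could be counted as low.

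**Rule.** A hematology white-cell PCSA occurs if any of these holds: WBC < 3.0 or ≥ 16.0; lymphocytes > 4.0; neutrophils < 1.5; monocytes > 0.7; basophils > 0.1; eosinophils > 0.5. These are the non-Black limits for WBC and neutrophils. The Black limits are lower, so they flag fewer low values.

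**Examples (Giga/L).**

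| Lymphocytes | Neutrophils | Monocytes | Eosinophils | Basophils | WBC (sum) | Rows met |
|---|---|---|---|---|---|---|
| 0.3 | 3.2 | 0.5 in total across these three | | | 4.0 | none |
| 0.4 | 4.0 | 0.5 | 0.2 | 0.05 | 5.15 | none |
| 0.2 | 4.0 | 0.5 | 0.2 | 0.05 | 4.95 | none |
| 0.0 | 2.5 | 0.4 | 0.2 | 0.02 | 3.12 | none |

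In the first line the other three cell types share 4.0 − 3.2 − 0.3 = 0.5. Monocytes and eosinophils therefore cannot exceed 0.7 and 0.5, and no row is met as long as basophils are at most 0.1. The last line is an extreme: no lymphocytes at all, and still no PCSA.

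**Why the WBC row cannot substitute.** WBC is the sum of the five cell types, so WBC ≥ neutrophils. If neutrophils are 3.0 or more, WBC is 3.0 or more whatever the lymphocyte count, and the low-WBC limit cannot be met.

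**The WBC comment has two possible readings.**

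1. It applies to the whole row. A differential is planned at every hematology test, so the row would normally not be interpreted at all.
2. It applies only to increases. The low limit then stays in use, but none of the four examples reaches it. A participant who did fall below 3.0 would be shown as low WBC, not as low lymphocytes.

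The gap remains on either reading.

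**After the change.** Under any low limit above 0.4 Giga/L, all four examples would be flagged.

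**The case against.** The strongest reply is that one row of one table is not the whole of laboratory safety:

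- SAP Appendix 4 shows that laboratory data also feed by-visit summaries, last on-treatment values and shift summaries.
- Protocol 8.2.4 has investigators record clinically significant laboratory changes as adverse events.
- Protocol 8.3.8 makes severe or opportunistic infection an event of special interest.
- An independent committee reviews safety data (Protocol 10.1.5.1).

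The antibody is also described as non-depleting, and no visible text lists lymphopenia among the potential risks. Appendix 6 is a sponsor standard, so tailoring it is partly a matter of preference.

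Most of this stands. A reader might infer that a fall in lymphocytes would go unseen, or that the drug is expected to cause one. The documents support neither. The other outputs could show a fall, and the mechanism text concerns memory T-cell survival signals, not the total blood count. Nor would the table report zero cases; it has no such row and would be silent.

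The reply leaves the central fact untouched. These other routes are not the stated incidence endpoint. Adverse event recording depends on investigator judgement, and summaries of means can hide a few very low individual values. Low limits for neutrophils and platelets show that the table already treats low counts as worth tabulating.

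**Conclusion.** The point holds as a limited gap: the PCSA incidence endpoint, as Appendix 6 defines it, cannot count a low lymphocyte value, and the low-WBC row does not substitute. The size within that endpoint is absolute, since no low value can be counted in any arm. The number of participants concerned is unknown, because the documents give no rate of low lymphocyte counts. The consequence is modest, because other outputs may reveal a fall.

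The conclusion assumes that Appendix 6 is the full set of criteria and that the redacted analysis text adds no low-lymphocyte category.

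A reader might go further and infer that the eosinophil row, an absolute limit of 0.5 Giga/L, would mostly record the asthma itself. The documents do not support that. They give the entry split at 300 cells/µL and not at 500, and any baseline handling would sit in redacted text. Stratification by eosinophil count and the placebo arm keep the comparison between arms valid. That reading is not part of this point.

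**What to change.** In SAP Appendix 6, add to the lymphocyte row a low category, defined as below the central laboratory's lower limit of normal, beside the existing limit of above 4.0 Giga/L. The sponsor may add one lower cut of its own choosing to separate marked from mild reductions. Apply the category at both the interim and the final analyses. If the redacted part of SAP 3.6.3.1 already provides for this, bring Appendix 6 into line with it.

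This is a tabulation category only and changes no eligibility or stopping rule. The cost is one table row and a few lines of programming on data already collected. There are two drawbacks. It departs slightly from the sponsor's standard list. Systemic steroid courses will also produce some low-lymphocyte flags. The placebo arm serves as the control for these, though less cleanly if steroid use differs between arms, so flags are best read beside steroid use.
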